## IV. Outcomes

**Primary Outcome:** The primary outcome for the pilot trial will be the Verbally administered Numeric Rating Scale (VNRS) for clinical pain measurement (0-100) at 30 minutes following randomized medication administration. 

Secondary Outcomes: Secondary outcomes will include adverse events including hypoxia needing supplemental oxygen (SpO2 < 90%); hypotension (systolic blood pressure < 90mmHg); advanced airway or bag mask ventilation; incidence of nausea/vomiting/headache/dizziness requiring treatment; serial (30 minute intervals until ED discharge, up to 120 minutes or rescue narcotic administration) measurements of a) VNRS for clinical pain (0-100), b) Patient Global Assessment (PGA) of Pain Control, c) Richmond Agitation-Sedation Scale (RASS) scores, and d) time-weighted Summed Pain Intensity Difference (SPID); number of rescue narcotic doses at 30 minutes and during ED stay (up to 120 minutes); time to a reduction in VNRS pain score of 10 points; patient cognitive function as assessed by the Six Item Screener (SIS) at 30 minutes; Healthcare Professional Global Assessment (HPGA) of the method of pain control at 30 minutes; and acceptability of pain treatment to health care providers.

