#### **Time-weighted Summed Pain Intensity Difference (SPID) at 30-minute intervals:**

Time-weighted SPID measurements will be calculated at approximate 30-minute intervals until discharge from the ED (up to 120 minutes) or rescue narcotic administration, will be determined when feasible. Essentially, the SPID represents serial assessments of pain intensity over time, weighted by time differences. SPID will be calculated using values from a 101-point continuous pain intensity scale (0 = no pain to 100= worst pain imaginable). The Pain Intensity Difference (PID) (e.g., raw differences in pain intensity) is calculated by subtracting the pain intensity at each time point from the pain intensity at time 0. The SPID is then calculated by multiplying the PID score at each post dose time point by the duration (in hours) since the preceding time point and then summing the values over the relevant time period. If patients did not complete the full 120 minutes, the last pain observation was carried forward.

#### Number of rescue doses of narcotic at 30 minutes and until ED discharge (up to 120

**minutes):** The number of doses of standard care pain treatment given within 30 minutes following randomly assigned intervention and total until ED discharge (up to 120 minutes), when feasible.

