## VI. Statistical Analysis Plan

Random Assignment: Participants will be randomly assigned in a 1:1 ratio to either DSUVIA or standard of care, stratified by site. Within each stratum, random assignment will be blocked, with random block size of two and four.

Analyses: All analyses will be carried out based on the intention-to-treat principle. Of those randomly assigned, the analyses will begin by describing the overall characteristics of the study population at the time of random assignment. Baseline characteristics will be described overall using summary statistics (e.g., means, standard deviation, percentages) and graphical techniques (e.g., histograms, box plots). Baseline characteristics between the two groups will be compared using t-tests or Wilcoxon tests for continuous variables and a chi-square tests for discrete variables.

The analyses for each aim are presented below.

AIM #1: To determine if, among injured patients with moderate to severe pain, treatment with DSUVIA compared to standard care pain treatment in the ED reduces the Verbally Administered Numeric Rating Scale (VNRS) for clinical pain measurement (0-100) at 30 minutes.

A t-test will be used to compare the mean VNRS scores between the two treatment groups. A multivariable regression model will be used to compare the means after adjusting for stratification

variables (i.e., site) and baseline characteristics not balanced through random assignment. All assumptions of the analyses will be tested (e.g., normality of residuals). If any assumptions are violated, transformations of the data will be investigated and the transformed data will be analyzed and evaluated. If an adequate transformation cannot be identified, nonparametric methods will be used.

AIM #2: To determine if, among injured patients with moderate to severe pain, treatment with DSUVIA compared to standard care pain treatment in the ED reduces adverse effects and events related to pain medication(s) including nausea/vomiting, headache, dizziness, hypoxia, hypotension, and need for advanced airway.

The adverse events will be analyzed in composite (any of them) and individually. For each, a chi-square test will be to compare the proportion of events between the two treatment groups. A multivariable logistic regression model will be used to compare the proportions after adjusting for stratification variables (i.e., site) and baseline characteristics not balanced through random assignment

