The DSMB will review the primary and secondary outcomes bi-annually. Prior to initiation of the trial, the final monitoring plan will be developed to serve as the guide to the DSMB's decision-making process concerning early stopping of the trial. The interim analysis will consist of two components, efficacy evaluation and futility evaluation. The purpose of the efficacy evaluation is to detect early sign of treatment effect early in the study. The purpose of the futility analysis is to assess if the study is unlikely to achieve a statistically significant effect. In making the decision to recommend termination of the study, the DSMB shall be guided by several types of information: (i) a formal stopping rule based on the primary analysis (comparison of treatment groups on the primary outcome), (ii) information on safety outcomes by treatment group, (iii) consistency between results for primary and secondary outcomes, (iv) consistency of treatment effects across subgroups, and (v) conditional power.

We have designed this trial with one-interim analyses before the final analysis. The number of interim analyses will be finalized in discussion with the DSMB prior to the initiation of the study. The interim analysis plan is based on the Lan and Demets approach utilizing an O'Brien-Fleming spending function to

determine alpha spending and test boundaries. A formal interim analysis of efficacy will be performed when 50% of the randomly assigned participants have completed the assessment of the primary outcome. We will use a t-test to test for difference. The level of significance will maintain an overall p-value of 0.05 according to O'Brien-Fleming stopping boundaries leaving a p value of 0.003 and 0.049 for the interim and final analyses, respectively. This translates to a two-sided z-value for the interim and final analyses of +/-2.96 and +/-1.97, respectively.

In addition, the futility of the study will be evaluated at the time an interim efficacy test is conducted. Specifically, the conditional power will be calculated. If the condition power is less than value prespecified by the DSMB (e.g., <20%), we can conclude that it would be futile to continue with the investigation.

Surveillance for Outcomes and Data Elements: Data will be collected prospectively as patient care progresses. This will include a review of the prehospital patient care report(s), ED and electronic/ paper hospital records.

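### The Aim 1 plan lets residual checks on the trial data decide whether the difference in mean 30-minute VNRS stays the primary analysis

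*Combined protocol and SAP*

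**What the plan says.** Section IV defines the primary outcome as the "Verbally administered Numeric Rating Scale (VNRS) for clinical pain measurement (0-100) at 30 minutes following randomized medication administration". For Aim 1, Section VI (Analyses) states: "A t-test will be used to compare the mean VNRS scores between the two treatment groups". It adds a regression adjusted for site and for baseline characteristics found to be unbalanced.

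All assumptions are then to be tested, with normality of residuals as the example. Two further steps follow:

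- The second step is a change of scale: "If any assumptions are violated, transformations of the data will be investigated and the transformed data will be analyzed and evaluated".
- The third step is the last resort, again with no method specified: "If an adequate transformation cannot be identified, nonparametric methods will be used".

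The Sample Size paragraph of Section VI works from an effect size of 0.45 and expresses the detectable effect as a difference between mean VNRS scores. For the interim look, Section VI (Interim Analyses) states: "We will use a t-test to test for difference". It gives no fallback there, and sets p = 0.003 at the interim and 0.049 at the final analysis.

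The only statement on how finely pain is scored is in the SPID definition in Section IV: "SPID will be calculated using values from a 101-point continuous pain intensity scale".

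**The concern.** Five choices about the primary analysis are left until the outcome data are in hand: the assumption check, its threshold, the candidate transformations, what makes a transformation adequate, and the nonparametric method. Nothing says that the mean difference stays primary once a check fails. The natural reading is that the later step replaces it.

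That matters for three reasons.

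- A contrast on a square-root or log scale, or a rank test, does not estimate the difference in mean VNRS that Aim 1 and the sample size concern.
- The interim and final looks could use different statistics under one pair of boundaries.
- A normality check at N = 150 reacts to features of a bounded verbal score, such as rounding, skew or pile-up at an end of the scale, that do little harm to a t-test with 75 per arm. The plan could drop its intended analysis for a reason that does not threaten its validity.

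**Working it through.** **1. The plan's own power.** Inputs from the Sample Size paragraph: effect size 0.45, 75 per group, two-sided 0.05. Normal approximation: power = Φ(0.45 × √(75/2) − 1.96) = Φ(2.756 − 1.960) = Φ(0.796) = 78.7%. The t-based value is 78.2%. The stated 80% is reproduced to within 2 points, and it is the power of a comparison of means. With SD 21, an effect of 0.45 is 0.45 × 21 = 9.45 points, which is used below. The plan's 7.1 points does not follow from these inputs; that is a separate matter.

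**2. How often a normality check fails.** Assumptions, not in the documents: scores are normal or beta-shaped and limited to 0-100; they are unrounded or rounded to tens; the check is run at 0.05. From the plan: 75 per arm, SD 21. There is no treatment difference, and 1,500 trials were simulated per setting.

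| Scores | Recorded | Shapiro-Wilk | Lilliefors | Skewness-kurtosis |
|---|---|---|---|---|
| Normal, mean 40-60 | unrounded | 4-13% | about 3% | 3-8% |
| Normal, mean 40-60 | tens | 59-80% | 90-91% | 2-9% |
| Normal, mean 70 | unrounded | 92% | 12% | 42% |
| Normal, mean 70 | tens | 100% | 96% | 40% |
| Beta, mean 40-70 | unrounded | 51-100% | 11-93% | 73-100% |
| Beta, mean 40-70 | tens | 92-100% | 95-100% | 67-98% |

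At mean 70 the upper limit is only (100 − 70)/21 = 1.43 SD away, so scores pile up at 100.

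Further runs with Shapiro-Wilk and mid-scale normal scores gave about 5% failing in whole numbers, about 9-12% in fives and about 53-63% in tens. A responder/non-responder mixture failed in 66-86% of trials even in whole numbers, and another mixture shape in 99% or more. Heaping at tens is therefore enough to trigger the switch under this check, but it is not necessary.

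**3. Where a failed check leads.** Square root, log(x + 1) and square were tried. With scores in tens, one of them restored normality in at most 0.4% of trials, so almost every failure ended at a rank test. With unrounded beta scores the figure reached 38% in one setting (mean 40), so a transformed scale can also be the end point.

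**4. Error rates, scores in tens.**

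| | Fixed t-test | Rule as written |
|---|---|---|
| Type I error | 4.0-6.0% | 3.8-5.5% |
| Power at 9.45 points | 76.5-78.7% | 75.1-78.8% |

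Monte Carlo standard error is about 0.6 points for type I error and 1.1 points for power. The two columns are practically the same.

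**5. Agreement of the two tests.** With a true difference, the t-test and the Wilcoxon test disagreed on significance in roughly 3-7% of simulated trials, depending on score shape.

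**6. Interim and final statistics.** If each test holds its own level, total type I error cannot exceed 0.003 + 0.049 = 0.052, whatever the two statistics are. The excess over 0.05 is at most 0.2 percentage points.

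**The case against.** A fair opponent would say that the order of steps is set in advance, that a check on pooled residuals favours neither arm, and that the rule leaves error rates intact. All of that stands for the rule applied mechanically. It does not answer the estimand problem, and the steps are ordered but not defined. The simulations do not measure what an analyst could do by choosing among transformations, so no figure is put on that.

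Four stronger readings are tempting, and the documents do not support them.

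- **The planned analysis will probably be lost because scores come in tens.** No section says that scores are given in tens; the SPID definition describes a 101-point continuous scale. No check is named either, and under a skewness-kurtosis check the failure rate can be 2% even with tens. A graphical check could not be simulated.
- **The rule inflates type I error or costs power.** Step 4 shows neither to any material degree.
- **The interim boundaries are invalidated.** The bound of 0.052 shows that the cost is negligible.
- **The result could not be given in VNRS points.** A rank test can be accompanied by a Hodges-Lehmann shift in VNRS points, and the plan does not say that the mean difference would go unreported. The shift is, however, a different quantity from the difference in means.

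It can also be said that adding baseline VNRS and robust standard errors goes further than the defect requires. That is partly right: the essential change is one sentence that keeps the mean difference primary. The fuller model is recommended because randomization is stratified by site and the baseline score is collected anyway.

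**Conclusion.** The concern holds as a weakness in pre-specification. As written, the trial's own residuals can move the primary analysis from the difference in mean VNRS to an unnamed transformed scale or an unnamed nonparametric method, away from the quantity behind the sample size and the interim t-test.

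The chance of a switch cannot be fixed from the documents. It runs from 2% to practically 100% over the score shapes, rounding and checks examined. The conclusion does not depend on that chance, because the rule stands in the plan whatever its frequency, and the t-test needs no such protection at 75 per arm. What is at stake is what the trial estimates and, in roughly 3-7% of trials with a true effect, which side of the significance line the result falls on. This should be corrected before the data are analysed; it does not threaten the validity of the trial.

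**What to change.** In Section VI (Analyses, Aim 1), state that the primary analysis is the difference in mean 30-minute VNRS on the 0-100 scale, whatever the residual checks show. Estimate it from a linear model with treatment, site and baseline VNRS, with heteroscedasticity-robust standard errors of a named type. Baseline VNRS is already collected: eligibility requires a pain score, and SPID uses pain at time 0.

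Delete the step that begins "transformations of the data will be investigated and the transformed data will be analyzed and evaluated". Name the Wilcoxon test as a sensitivity analysis, and report residual checks as description only.

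In Section VI (Interim Analyses), replace the t-test by the same model-based statistic, so that both looks test the same quantity against the stated boundaries.

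The cost is SAP wording only. Data collection and the planned 150 participants do not change.

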## I. Objective and Specific Aims

Our objective is to perform a prospective, randomized, interventional trial of Emergency Department (ED) administration of DSUVIA versus standard care pain management comparing pain treatment outcomes in injured patients with moderate to severe pain.

**AIM #1:** To determine if, among injured patients with moderate to severe pain, treatment with DSUVIA compared to standard care pain treatment in the ED reduces the Verbally administered Numeric Rating Scale (VNRS) for clinical pain measurement (0-100) at 30 minutes.

Hypothesis #1: Null Hypothesis: There will be no difference in the pain score at 30 minutes of patients who received DSUVIA as compared to standard care pain medicine in trauma patients

**AIM #2**: To determine if, among injured patients with moderate to severe pain, treatment with DSUVIA compared to standard care pain treatment in the ED reduces adverse effects and events related to pain medication(s) including nausea/vomiting, headache, dizziness, hypoxia, hypotension, and need for advanced airway.

Hypothesis #2: Null Hypothesis: There will be no difference in the rate of adverse events of nausea/vomiting, headache, dizziness, hypoxia, hypotension and need for advanced airway in patients who received DSUVIA as compared to standard care pain medicine in trauma patients.

**AIM #3:** To determine if, among injured patients with moderate to severe pain, treatment with DSUVIA compared to standard care pain treatment in the ED improves pain treatment effectiveness including serial VNRS scores (every 30 minutes), the need for rescue narcotic administration, the time needed to reduce the VNRS pain score by 10 points, time-weighted summed pain intensity difference, patient global assessment (PGA), Six Item Screener (SIS) cognitive assessment and Richmond Agitation-Sedation Scale scores.

Hypothesis #3: Null Hypothesis: There will be no difference in the pain treatment effectiveness, need for rescue narcotic administration, time to reduction of 10 points of VNRS pain score by 10 points, the time-weighted summed pain intensity difference, patient global assessment, Six-Item Screener and the Richmond Agitation-Sedation Scale scores in patients who received DSUVIA as compared to standard care pain medicine in trauma patients.

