The NAEMSP guidelines focus on intravenous (IV) fentanyl and morphine because of wide availability among American EMS services. Use of IV opioids is limited by the need to obtain IV access, which can be time consuming, is associated with a significant failure rate, and may lead to increased exposure in a tactical environment. The US military uses oral transmucosal fentanyl citrate (OTFC) which can be administered without IV access, but has slow absorption. Furthermore, safety data on OTFC, outside of long-term analgesia for cancer patients, is not well described. Given these significant limitations, an alternative to IV opioid analgesics in necessary. The ideal agent has robust stability, easy delivery, rapid onset, minimizes altered mental status and has a wide therapeutic index. In addition, the ideal agent would have a longer duration of action and an improved side effect profile as compared to the current standard care.

Sufentanil is a potent opioid analgesic derived from fentanyl with no active metabolites, rapid onset, and a therapeutic index superior to morphine and fentanyl. Sufentanil is highly lipophilic and rapidly achieves equilibrium in the brain; the time to analgesia is similar to IV morphine. When administered sublingually, sufentanil is 53% of the IV bioavailability within one minute and provides analgesia within 15 minutes. Sufentanil has a low incidence of side effects, with nausea, headache, dizziness, and vomiting being the most common. As with any opioid, respiratory depression and hypoxia can occur but was observed to be <1%. Similar studies found no clinically significant changes in vital signs after the administration of sublingual sufentanil in post-operative patients. Sufentanil was effective in a cohort of patients with painful injuries presenting to the ED with pain reduction seen in less than 15 minutes and persisting for 2 hours.

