#### Secondary Outcome Definitions:

**Hypoxia, hypotension or need for advanced airway:** The principal safety outcome for the trial will be the incidence of serious adverse events following the first dose of analgesic following randomization including hypoxia (SpO2 < 90%), hypotension (SBP < 90 mmHg) or the need for advanced airway management (placement of an endotracheal tube, supraglottic airway or bag mask ventilation) until ED discharge (up to 120 minutes), when feasible.

Composite outcome of nausea, vomiting, headache, and/or dizziness requiring treatment: The incidence of nausea, vomiting, headache, and/or dizziness requiring treatment will be recorded for initial 30 minutes, when feasible.

Verbally administered Numeric Rating Scale (VNRS) pain measurements (0-100) at 30- minute intervals: VNRS for clinical pain (0-100) measurements at approximate 30-minute intervals until discharge from the ED (up to 120 minutes) or rescue narcotic administration, will be obtained when feasible.

**Patient Global Assessment (PGA) of Pain Control at 30-minute intervals:** The PGA of the method of pain control at approximate 30-minute intervals until discharge from the ED (up to 120 minutes) or rescue narcotic administration, will be obtained when feasible. The research team will read the following statement aloud to the subject and the response will be recorded: "Overall, would you rate this method of pain control during the last 30 minutes/hours as being poor (1), fair (2), good (3), or excellent (4)?"

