# AIM #4: To determine if, among injured patients with moderate to severe pain, treatment with DSUVIA compared to standard care pain treatment in the ED improves Healthcare Professional Global Assessment (HPGA) of the Method of Pain Control and health care provider survey scores.

Scores to the HPGA will be based on a four-point scale. A 2x4 chi-square test will be used to compare the distribution of scores across the two treatment groups. An ordinal polytomous logistic regression model will be used to compare the distribution of proportions after controlling for stratification (sites) and baseline characteristics not balanced through random assignment. The same analysis will be repeated on the health care provider survey scores, with the modification to account for a five-level outcome.

**Sample Size**: The sample size calculations are based on the analyses of the primary aim (Aim 1) of the study. To detect a minimum effect size of 0.45, a sample size of 150 subject is needed (75 per group), assuming a type I error of 0.05, a two-sided alternative hypothesis, and 80% power. Thus, assuming a standard deviation of 21 (Karcioglu, 2003), a difference of 7.1 can be detected between the mean VNRS scores.

**Missing data**: Every attempt will be made to minimize the amount of missing data. Give the short timewindow to collect data, missing data should be minimal. However, in the event that there is missing data for the outcomes, the pattern of missingness will be evaluated. Assuming that the data will be missing at random, multiple imputation techniques will be used to impute data and carry out the proposed analyses.

**Subgroup**: Analyses will be carried out for pre-defined subgroups, specifically: sex (male/female), Injury Severity Score (ISS < or  $\ge 16$ ), age (< or  $\ge 50$ ), blunt versus penetrating injury, history of prior opioid use (Y/N), air versus ground prehospital transport, transport origin (scene versus outside ED). For all subgroup analyses, regression models will be used to assess if there is a differential treatment effect by subgroup. Regression models will include main effects for treatment and the indicator of the subgroup, as well as the two-way interaction between treatment and the subgroup indicator. A statistically significant interaction will indicate a differential treatment effect.

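### The plan names a principal safety outcome (hypoxia, hypotension or advanced airway) but states no between-arm test of it; the only planned composite also pools in treated symptoms

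*Combined protocol and SAP*

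**What the plan says.** The Secondary Outcome Definitions in section IV set out two safety outcomes.

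- **Principal safety outcome.** The text reads: "The principal safety outcome for the trial will be the incidence of serious adverse events following the first dose of analgesic". Its events are hypoxia, hypotension or the need for advanced airway management, with the window given at the end of the definition: "supraglottic airway or bag mask ventilation) until ED discharge (up to 120 minutes), when feasible".
- **Symptom composite.** Nausea, vomiting, headache and/or "dizziness requiring treatment will be recorded for initial 30 minutes, when feasible".

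Hypothesis #2 in section I puts both groups of events in one list: "There will be no difference in the rate of adverse events of nausea/vomiting, headache, dizziness, hypoxia, hypotension and need for advanced airway".

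The Aim #2 analysis in section VI repeats that list and says: "The adverse events will be analyzed in composite (any of them) and individually". Each comparison gets a chi-square test and a logistic model adjusted for site and unbalanced baseline characteristics. The text does not mention the principal safety outcome, a time window, or the condition that symptoms require treatment.

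**The concern.** Aim 2 is the trial's between-arm safety comparison. If the plan is followed as written, the outcome that the protocol calls principal is never compared between arms in the form in which it is defined. The one composite that is tested asks a broader question, because it counts a patient with treated nausea the same as a patient with hypoxia.

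Two things are at stake. A real difference in the principal outcome can be diluted by symptom events that are equally common in both arms. And with no principal safety comparison named in the analysis section, emphasis among the pooled result, the single events and the defined outcome could be chosen after the data are seen. In an open-label trial that choice is better fixed beforehand.

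**Working it through.** **1. Definitions against analysis.**

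| Outcome | Defined in section IV | Test stated in section VI, Aim #2 |
|---|---|---|
| Hypoxia, hypotension or advanced airway, combined | Yes, as the principal safety outcome | None |
| Hypoxia, hypotension and airway, each singly | Listed under Secondary Outcomes | Yes (*individually*) |
| Treated nausea, vomiting, headache and/or dizziness | Yes, as a composite | Not named; arguably covered by *individually* |
| Any of the six event types | No | Yes (*any of them*) |

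The rest of section VI does not fill the first row. Aim #3 borrows the Aim 2 methods for its own binary outcomes. Interim Analyses refers only in general terms to safety information by arm.

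**2. Inputs.** The plan gives 75 per arm, two-sided 0.05 and a chi-square test. It gives no rate or power for either composite, so there is no plan figure to reproduce and every composite rate below is assumed. Power is by exact enumeration of both binomials, rejecting when Pearson chi-square exceeds 3.841.

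**3. Dilution.** Let p be the principal-outcome risk and m the symptom risk, the same in both arms and independent of p. The pooled risk is 1 − (1 − p)(1 − m). For p = 5% and m = 10%: 1 − 0.95 × 0.90 = 14.5%. For p = 15%: 1 − 0.85 × 0.90 = 23.5%.

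| Symptoms, both arms | Pooled risk, 5% v 15% | Power | Pooled risk, 2% v 6% | Power |
|---|---|---|---|---|
| Not pooled | 5% v 15% | 55% | 2% v 6% | 22% |
| 1% | 5.95% v 15.85% | 51% | 2.98% v 6.94% | 19% |
| 3% | 7.85% v 17.55% | 44% | 4.94% v 8.82% | 16% |
| 10% | 14.5% v 23.5% | 29% | 11.8% v 15.4% | 10% |
| 30% | 33.5% v 40.5% | 15% | 31.4% v 34.2% | 7% |

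The last entry is 6.65% with the cut-off 3.841 and 6.4% with 3.8415, because one pair of possible results lies between the two. The loss is small if treated symptoms are rare and large if they are common.

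**4. What the single-event tests recover.** Split the same totals over three non-overlapping events.

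| | 2% v 6% | 5% v 15% |
|---|---|---|
| Combined outcome | 22% | 55% |
| Excess spread equally: each test | 4% (0.67% v 2%) | 19% (1.67% v 5%) |
| Excess spread equally: any of three significant, unadjusted (simulated) | 11% | 46% |
| Excess all in one event: that test | 30% (0.67% v 4.67%) | 75% (1.67% v 11.67%) |

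The single-event tests do better than the combined outcome when the excess falls in one event and worse when it is spread.

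**5. Rare events.** Section II reports respiratory depression and hypoxia with sufentanil below 1%. Assume the same hypoxia rate in both arms. The chance that at least one arm of 75 has no event is 1 − (1 − (1 − r)^75)²:

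- r = 1%: 0.99^75 = 0.471, giving 1 − 0.529² = 72%.
- r = 0.5%: 0.995^75 = 0.687, giving 1 − 0.313² = 90%.

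Where an arm has no events, ordinary logistic regression gives no finite treatment estimate.

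**6. Precision.** With 3/75 v 3/75, the Newcombe score 95% interval for the risk difference is −7.6 to +7.6 points.

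**The case against.** The best defence is that *individually* may mean each outcome as defined, and that no component is left out. Part of this stands.

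- **Symptom composite.** A reader might infer that this composite also lacks a test. The documents do not support that firmly. The Secondary Outcomes list in section IV gives the four symptoms as a single item, so *individually* can fairly be read to cover it. The Aim #2 text lists the symptoms separately, so a clarifying sentence is still useful.
- **Principal outcome.** It might be read as three separate incidences, since only the symptom group is labelled a composite. That is the weaker reading: the definition speaks of one outcome and one incidence, with its events joined by *or*.
- **The pooled composite.** A reader might infer that it is an error and should become descriptive only. It matches Aim 2 and Hypothesis #2, which list all the events together, so it answers a stated question. That it mixes a 30-minute and a 120-minute window is inferred from the definitions; the analysis text gives no window.
- **Opposite effects.** A reader might infer that the pooled test would hide harm. Rates can be chosen that cancel: principal 5% v 15% with symptoms 20% v 10% gives 1 − 0.95 × 0.80 = 24.0% v 1 − 0.85 × 0.90 = 23.5%. Nothing in the documents suggests that pattern.
- **Modest consequence.** This also stands. The sample size rests on Aim 1 ("The sample size calculations are based on the analyses of the primary aim (Aim 1) of the study"), the added test has low power, the single events are compared, and the DSMB sees safety by arm.

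**Conclusion.** The gap is real but narrow. The combined outcome that the protocol calls principal has no stated between-arm test, and the planned pooled composite is a different endpoint that can dilute it. At the assumed 5% v 15%, power falls from 55% to between 51% and 15% as symptom rates rise from 1% to 30%. At 2% v 6% it falls from 22% to between 19% and about 7%.

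These sizes depend on assumed rates, independence of symptoms from the principal events, and equal symptom rates in the two arms. The mismatch between definition and analysis depends on none of them. It would be too strong to say that serious safety events go uncompared, since each component has its own test. The change should be made, but it does not affect the primary endpoint.

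**What to change.** In section VI, Analyses, Aim #2:

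1. Add the principal safety outcome from the Secondary Outcome Definitions as its own endpoint, over its stated window, and name it as the principal safety comparison.
2. State that the composite of symptoms requiring treatment in the first 30 minutes is one of the outcomes tested *individually*.
3. Keep the single-event and *any of them* analyses as secondary.
4. Report counts and risk differences with score confidence intervals, and use penalised (Firth) logistic regression for the adjusted analysis where an arm has no events.

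Separately, reconcile the hypoxia wording. The Secondary Outcomes list and Study Risks and Benefits (section IX) attach a need for oxygen to the saturation threshold; the Secondary Outcome Definitions use the threshold alone.

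The cost is wording, one more composite test and slightly more analysis, with no new data, visits or patients. The change does not cure low power: at 75 per arm a non-significant result must not be reported as equal safety.
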